Our central hypothesis is that a targeted CRC screening strategy will lead to higher screening uptake. To complete this study, we will leverage electronic health record data and primary data from average risk adults ages 45-49 receiving care at University of California, San Diego Health System (UCSDHS). We plan to include adults ages 45-49 receiving care at UCSDHS, with an assigned primary care provider (PCP) at UCSDHS, currently not up to date with CRC screening and without prior colonoscopy or personal history of inflammatory bowel disease, polyps or CRC. For interviews, we will recruit eligible adults ages 45-49 and providers to answer questions about potential patient-, provider- and system-related factors relevant to CRC screening uptake specific to adults ages 45-49. Our pilot trial intervention will be mailed multi-target stool DNA test outreach, which in survey data has been found to be preferable in individuals under age 50 when offered a choice of screening tests. The pilot trial control group will be mailed fecal immunochemical test outreach, which has been proven highly effective at increasing screening uptake, particularly among underserved populations. Equipoise exists as to the best approach for offering CRC screening outreach, because both of these tests are guideline recommended for screening but have not been compared head-to-head in a randomized trial to determine whether offering one strategy may be superior to the other. Our primary trial outcome is completion of CRC screening using any USPSTF-recommended modalities within 3 months of date of randomization.

Our study will be the most comprehensive examination of early CRC screening initiation in the US to date and will provide context to the updated CRC screening policy and a potential framework for wider implementation of earlier CRC screening in adults ages 45-49.

Introduction and Background

A. Introduction

1. Colorectal cancer is a growing public health problem burden among adults ages <50.

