Colorectal cancer (CRC) is the second leading cause of cancer death in the United States (US), with 11% of cases diagnosed before age 50—known as early age onset CRC (EOCRC).¹ CRC risk increases with age and disproportionately affects men, Black and American Indian and Alaska Native (AI/AN) racial/ethnic groups and persons with limited healthcare access or low socioeconomic status (SES).^{2–5} While CRC incidence and mortality have decreased in adults ages ≥50, EOCRC incidence and mortality have increased steadily.⁶ By 2030, an estimated 10% of colon and 22% of rectal cancers will be EOCRC cases, making preventive strategies and earlier CRC detection crucial.⁷ CRC screening is seen as a major driver of decreases in CRC incidence and mortality in adults ages ≥50.^{6,8} The rising EOCRC morbidity and mortality burden and the evidence among adults ages ≥50 of CRC screening efficacy were the impetus for the recent US Preventive Services Task Force (USPSTF) recommendation to initiate CRC screening in average risk adults at age 45 rather than 50.

2. USPSTF updates assume perfect screening participation despite imperfect uptake.

The significant update to the USPSTF CRC screening guidelines is mainly supported by cancer screening modeling which assumes perfect participation in screening. These models predicted earlier CRC screening at 45 could prevent up to 3 additional CRC cases and 2 CRC deaths and lead to 15-34 life-years gained per 1000 persons screened.⁹ While USPSTF projections of potential benefit rely on prior screening studies in adults ages ≥50, the modeling additionally assumes 100% participation in screening to calculate predicted benefits.^{10,11} This assumption is problematic, as only 68% of US adults ages 50-75 are up-to-date with CRC screening, with only 48% of adults ages 50-54 reporting being up-to-date, and early evidence of CRC test prevalence among adults ages 45-49 only reaching 21%.^{1,12–14} In addition to age-related

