- Lives within San Diego or Imperial County (via Residential Zip Code)
- Currently not up to date with CRC screening
- Insured by private health insurance, public health insurance (i.e., Medicaid [Medi-Cal]) or other health insurance

Provider Participants

- Physicians or Advanced Practice Providers (i.e., Nurse Practitioners and Physician Assistants) involved in referral to CRC screening. Providers eligible for participation in this study will include those who practice in the following specialties:
 - Primary Care
 - Obstetrics/Gynecology
 - Gastroenterology
 - Oncology

The specific exclusion criteria for Aim 1 are:

Patient Participants

- Up to date with CRC screening, including:

- Colonoscopy within past 9.5 years
- Sigmoidoscopy within the past 5 years
- CT colonography within the past 5 years
- gFOBT or FIT in the past 10 months
- Stool DNA test within the past 3 years
- Prior history of colonic disease including:
 - Inflammatory bowel disease (e.g. ulcerative colitis or Crohn's disease)
 - One or more colorectal neoplastic polyps (i.e., adenomas)
 - Colorectal cancer
- Prior colectomy
- Lack of health insurance

Provider Participants

- Less than 1 year practice experience at UCSDHS

Aim 2. Pilot Trial

The specific inclusion criteria for Aim 2 are:

- Adults ages 45-49
- EHR documentation indicating the patient has an assigned primary care provider at UCSDHS
- ≥1 UCSDHS health visit within the last year
- Lives within San Diego or Imperial County (via Residential Zip Code)
- Currently not up-to-date with CRC screening
- Insured by private health insurance, public health insurance (i.e., Medicaid [Medi-Cal]) or other health insurance

The specific exclusion criteria for Aim 2 are:

- Up-to-date with CRC screening, including:

- Colonoscopy within past 9.5 years
- Sigmoidoscopy within the past 5 years
- CT colonography within the past 5 years
- gFOBT or FIT in the past 10 months
- Stool DNA test within the past 3 years
- Prior history of colonic disease including:
 - Inflammatory bowel disease (e.g. ulcerative colitis or Crohn's disease)
 - One or more colorectal neoplastic polyps (i.e., adenomas)
 - Colorectal cancer
- Prior colectomy
- Lack of health insurance

1. Identification of Candidate Patients and Recruitment.

Aim 1. Interviews

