We will identify relevant exclusion criteria through the UCSDHS EHR based on previously defined algorithms (**Table 1**). Prior colonoscopy (reflecting up to date CRC screening) will be identified using Current Procedure Terminology (CPT) codes. History of IBD, CRC and colorectal adenomas will be identified using International Classification of Diseases, 9th and 10th editions (ICD-9/10). We will also confirm exclusion criteria by examining problem lists and other EHR data sources (such as the EHR health maintenance registry) with structured queries.

Table 1. Study Exclusion Criteria

Exclusion Criteria	Codes
Up to Date with CRC Screening	Colonoscopy CPT: 44388-44394, 44397, 44401-44407, 45355, 45378-45393, 45398, G0105, G0121, G6019, G6020, G6024-G6025 Stool Blood Test CPT: 81528, 82270, 82274, G0328, G0464 Sigmoidoscopy CPT: 45330-45335, 45337-45338, 45346-45347, 45340-45342, 45349-45350, G0104
History of Inflammatory Bowel Disease	ICD-9: 555.9, 560.89; ICD-10: K52.9
History of Colorectal Adenomas	ICD-9: V12.72; ICD-10: Z86.010
Prior colorectal cancer	ICD-9: 153.0-153.9, 154.0-154.3, 154.8; ICD-10: C18.0, C18.2-C18.9, C19.9, C20

C. Intervention Regimens and Rationale

1. Mailed multi-target stool DNA (Cologuard) test outreach.

The intervention to be tested in the pilot is mailed Cologuard outreach, a multi-component strategy that has been proven to be a highly acceptable test among current screening-eligible adults.^{35,36} Cologuard is a USPSTF-recommended at-home screening test for blood in stool that additionally examines DNA markers in the stool to detect cancer. Its sensitivity to detect CRC is 92% and specificity is 87%.³⁷ Abnormal Cologuard results are followed up with a colonoscopy to identify and remove pre-cancerous polyps or diagnose early-stage CRC. [name] will be the ordering provider of the Cologuard tests for those participants randomized to the mailed Cologuard outreach. Participants randomized to mailed Cologuard outreach will receive:

- 1) advanced notification (primer) via mail one week prior to receiving the Cologuard test;
- 2) Cologuard test shipped directly to patient's home, with 2 months of personalized support to facilitate screening completion included. Included with the Cologuard test is a collection kit that may be returned at no cost to the patient via UPS (either by contact-free pick-up or drop-off at UPS). The Cologuard Customer Care Center also is available via phone or chat to aid with test completion.

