- 3) Patient results will be sent to the ordering provider within 2 weeks of test completion and return.

Patients with normal results will be sent a letter to repeat CRC screening in 3 years. Patients with abnormal results will be sent a letter encouraging follow up colonoscopy, and their primary care provider will be notified and requested to order colonoscopy. Patients with colonoscopy orders will receive usual care colonoscopy scheduling, preparation, and completion by the UCSDHS GI department. Notably, some clinicians at UCSDHS are already offering Cologuard as a usual care screening test.

2. Mailed fecal immunochemical test (FIT) outreach.

The control group to be tested in the pilot is mailed FIT outreach, a multi-component strategy found to have the largest effect size to improve CRC screening uptake compared to usual care.^{35,36} FIT is a USPSTF-recommended at-home screening test for blood in stool. Abnormal FIT results are followed up with a colonoscopy to identify and remove pre-cancerous polyps or diagnose early-stage CRC.³⁴ FIT test kits will be prepared at UCSD Health to be delivered to participants randomized to this study arm. Participants randomized to mailed FIT outreach will receive:

- 1) advanced notification (primer) via mail one week prior to receiving the FIT kit;
- 2) FIT kit normally offered at UCSDHS (Polymedco OC Light) with study information, invitation and instructions to complete FIT and how to opt-out; and
- 3) reminders via mail 14 days and 28 days after FIT kit receipt.

FIT kits will be mailed to UCSD Health System to undergo current usual care assay and reporting, based on the Polymedco OC Light criteria (the current test used within UCSDHS). Patients with normal results will be sent a letter to repeat CRC screening in a year. Patients with abnormal results will be sent a letter encouraging follow up colonoscopy, and their primary care provider will be notified and requested to order colonoscopy. Patients with colonoscopy orders will receive usual care colonoscopy scheduling, preparation, and completion by the UCSDHS GI department.

D. Outcome Measures and Rationale

1. Aim 1 Interview Constructs

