To ensure potential participants are eligible for our pilot trial, we will assess patient participant eligibility criteria at the point of recruitment to ensure that they qualify for colorectal cancer screening. This will limit the likelihood of incurring costs by ensuring the patient is age-eligible, does not have any of the excluding risk factors, and has not received prior screening or diagnostic testing that precludes them from receiving one of the screening tests in our study.

Protection of provider participants from intimidation or coercion to participate.

We are particularly interested in the perspectives of providers actively involved in referral to and coordination of colorectal cancer screening at UCSDHS. These providers will offer important information on barriers and facilitators of colorectal cancer screening among adults ages 45-49, who are newly eligible based on updated screening guidelines. The provider perspective offers additional context to better understand the various factors ultimately impacting screening uptake. Providers will be directly recruited to participate and will have autonomy to choose whether they wish to participate. They will not be coerced or intimidated into participation. Measures to prevent coercion will include not allowing a provider's supervisor to know who elected to participate or not (anonymizing the provider if they agree to participate) and assuring providers that deciding to participate will not have a negative effect on that provider's job or standing at work. Provider participant responses to interviews will be anonymized, such that they cannot be traced back to a specific provider participant. When presenting research findings, all provider participants will be referred to as "providers" when discussing their responses, such that there is no way to trace back individual responses to an individual provider or someone within a specific discipline.

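### Aim 2 eligibility screens earlier stool tests by date and not by result, so a person with an old abnormal FIT or gFOBT and no colonoscopy can be mailed another kit

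*Combined protocol and SAP*

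**What the plan says.** The Aim 2 exclusion list appears twice in the combined protocol and SAP: under Study Population and Rationale (Summary of the Study Design, B) and under Inclusion and Exclusion Criteria (Patient Population, B). In both places, being up to date is defined by test type and a time window. For blood-based stool tests the rule is "gFOBT or FIT in the past 10 months". For stool DNA the window is 3 years and for colonoscopy 9.5 years. The remaining exclusions are inflammatory bowel disease, adenomas, colorectal cancer, colectomy and lack of insurance. No line refers to the result of an earlier stool test.

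Table 1 (Exclusion Criteria Data Ascertainment) finds earlier stool tests by procedure code: "Stool Blood Test CPT: 81528, 82270, 82274, G0328, G0464". The text adds that problem lists and the health maintenance registry will be used to confirm the exclusions.

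Intervention Regimens and Rationale gives the pathway for kits returned in the trial. "Abnormal FIT results are followed up with a colonoscopy to identify and remove pre-cancerous polyps or diagnose early-stage CRC", and the same is said of Cologuard. After a normal Cologuard, "Patients with normal results will be sent a letter to repeat CRC screening in 3 years". After a normal FIT, "Patients with normal results will be sent a letter to repeat CRC screening in a year".

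Three other places bear on intent. The Executive Summary speaks of "primary data from average risk adults ages 45-49 receiving care at University of California, San Diego Health System". The partial HIPAA waiver lists screening test documentation among the data viewed at recruitment. Protection Against Risk says eligibility will be assessed so that the person "has not received prior screening or diagnostic testing that precludes them from receiving one of the screening tests in our study".

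**The concern.** A rule based on dates treats an old abnormal test and an old normal test alike: once the window has passed, both people are due for screening. That is right after a normal test. After an abnormal one the person is overdue for colonoscopy, and the protocol itself names colonoscopy as the next step.

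What is at stake is participant safety in a small number of people. Someone who already needs colonoscopy could receive a second stool kit and then a study letter that reads as reassurance for 1 or 3 years. The protocol recognises this type of problem for its own kits. Under Aim 2 Secondary Outcomes it plans chart review at 3, 6 and 9 months and messages to the PCP when an abnormal study kit has not led to colonoscopy. It has no matching rule for a person who enters the trial in that state.

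**Working it through.** The plan states no figure on this point, so there is none to reproduce. The check applies the listed criteria to a case and then follows that case through the trial.

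**Step 1. Apply the criteria.** Take an insured 47-year-old with an assigned PCP, a visit in the last year and an eligible home address, who had an abnormal FIT 14 months ago and no colonoscopy or other test since.
- Inclusions: all met. The person counts as not up to date because 14 months is more than 10 months.
- Colonoscopy, sigmoidoscopy, CT colonography and stool DNA windows: none apply.
- Bowel disease, adenoma, cancer, colectomy, lack of insurance: none apply.
- Table 1 codes: these show that a FIT was done, not what it found.

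The person is eligible. Had the same abnormal FIT been 8 months ago, the person would have been excluded, but as up to date, which confirms that the rule reads the date and not the result.

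**Step 2. The stool DNA route.** The same gap exists for an abnormal stool DNA test more than 3 years ago, but it is less plausible. Participants are under 50, so such a test was done before age 50 − 3 = 47. The recommendation the protocol cites is to "initiate CRC screening in average risk adults at age 45 rather than 50". For the test to have been routine screening at 45 or later, the person must now be at least 45 + 3 = 48. Only those aged 48 or 49 could qualify this way.

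**Step 3. What happens after enrolment.**
- Kit not returned: no letter, and no follow-up of an abnormal study result.
- Kit returned and abnormal: letter, PCP notification and the chart-review pathway. This could speed up colonoscopy.
- Kit returned and normal: a letter setting repeat screening at 12 months (FIT) or 36 months (Cologuard).

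**Step 4. How the last two split, given cancer and a returned kit.** Inputs are the protocol's sensitivities: FIT 74% and Cologuard 93% (Introduction, A.3), and Cologuard 92% (Intervention Regimens and Rationale, C.1).
- Abnormal repeat = sensitivity: FIT 0.74; Cologuard 0.92 to 0.93.
- Normal repeat = 1 − sensitivity: FIT 1 − 0.74 = 0.26; Cologuard 1 − 0.93 = 0.07 to 1 − 0.92 = 0.08.

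This assumes that the repeat result is independent of the first. A cancer that already gave one abnormal test is more likely to give another, so the normal shares are probably upper figures.

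**Step 5. Frequency.** Sample Size and Rationale shows that mailed FIT outreach to people aged 45 to 49 has already taken place in this health system, so the route exists. It gives no dates, coverage, abnormal rate or follow-up rate. No unconditional risk can be computed.

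**The case against.** The strongest reply is that Protection Against Risk already covers the case. If an abnormal stool test calls for colonoscopy, it is earlier testing that rules out a study kit, and the records needed to see it are already in scope. This stands in part: a careful chart reader could stop such a person on that sentence. But it sits under protection from insurance costs, names no result and gives no operating rule, and the problem-list and registry checks confirm listed exclusions, of which this is not one.

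The second reply is that net harm is not shown. This stands. Everyone eligible has a PCP and a visit in the last year, so where the abnormal test is more than 12 months old, a visit came after it. The health system has a referral route for abnormal screenings. The study letter cancels no referral, and most repeat kits in people with cancer would be abnormal and enter follow-up.

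Stronger readings are tempting, and the document does not support them:
- *The protocol contradicts itself.* It does not. The colonoscopy pathway is written for kits returned in the trial, and the criteria are silent on earlier results. This is a gap.
- *The exclusion list is declared complete.* The section on inclusion of women and minorities summarises exclusions as if they were the only ones. That summary omits colectomy and is inconsistent about earlier colonoscopy, so it proves nothing about completeness.
- *Colonoscopy would be delayed by 1 or 3 years.* Those are intervals in a letter. Whether the letter displaces colonoscopy is a risk, not an outcome that can be read off the plan.
- *The comparison is biased.* Assignment is random within race/ethnicity groups, so no difference between arms is expected from this source.

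**Conclusion.** The gap is real and the point is a cheap improvement. Both Aim 2 lists and the Table 1 codes admit a person with an abnormal FIT or gFOBT more than 10 months ago and no later colonoscopy and, less plausibly, one with an abnormal stool DNA test more than 3 years ago. A normal study kit would then bring a repeat-screening letter at 1 or 3 years.

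The number of such people cannot be estimated and is likely small in a pilot of 100. The 26% (FIT) and 7 to 8% (Cologuard) are conditional on cancer, on kit return and on independence from the first test, and say nothing about how often the situation arises. No effect on the primary comparison is claimed. The conclusion rests on the wording of the criteria and on the fact that a procedure code carries no result.

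**What to change.** Add one line to both Aim 2 exclusion lists: *earlier abnormal FIT, gFOBT or stool DNA test without a later completed colonoscopy*.

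Apply it with a single result check, after signed consent and HIPAA authorization and before randomization, only in people whose record shows an earlier stool test. Checking everyone before consent is heavier than needed. It could also drop people with no alert to anyone, because data viewed under the partial waiver may be used only for recruitment.

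For anyone flagged:
- send the PCP an alert modelled on the one under Aim 2 Secondary Outcomes, so that exclusion does not remove follow-up;
- replace the person within the same race/ethnicity stratum, as the recruitment section already does for those who decline;
- report the number flagged, which also gives the larger trial the frequency that is missing now.

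The cost is a short chart check for a subset of consented people, possibly a few replacements, and a small IRB modification to cover the new criterion and the alert before randomization. The document does not say whether results, especially from outside records, can be returned by query, so some checks may be manual.

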For interviews, we plan to recruit 20 adults ages 45-49, as well as 10 UCSDHS providers involved in CRC screening referral and coordination, including primary care providers, obstetricians or gynecologists, gastroenterologists and oncologists. Participants will be selected by applying a stratified random sampling method to ensure equitable representation from the five major racial and ethnic groups. Selected participants will be contacted via e-mail about the study with directions to schedule a time for their interview, if they are interested in participating. Scheduling of interviews will occur using Calendly platform, allowing patients to directly choose a time slot in the interviewer calendar based on their availability. Participants will be asked to provide their name and email address to schedule an appointment. Provider participants will be recruited via convenience sampling and contacted directly via email about the study with directions to schedule a time for their interview, if they are interested in participating. Scheduling of interviews will occur using Calendly platform, allowing patients to directly choose a time slot in the interviewer calendar based on their availability. Provider participants will be asked to provide their name and email address to schedule an appointment.

As our Aim 2 pilot trial is a feasibility study, the sample size is not projected to ensure study power for hypothesis testing. We instead assess precision of our primary outcome, CRC completion in 3 months, based on a projected sample size of 100 (50 per study group; 10 per race/ethnicity group) and a two-sided type I error alpha of 0.05. Based on this sample, we will have 80% power to detect a ≥ 15 percentage point higher rate of completion in the Cologuard group than the mailed FIT outreach group, assuming that the completion rate in the mailed FIT group is 23%. The assumption of mailed FIT completion is based on internal, UCSDHS data from prior mailed FIT outreach in 45 to 49 year olds.

Patient Population

A. Recruitment and Screening Strategy

Aim 1 Interviews

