Using the UCSDHS EHR, we will conduct a query for a list of all potential participants who meet the eligibility criteria. We will use both Epic and Care Everywhere platforms to ascertain eligibility criteria for recruitment. Among the list of adults deemed eligible for recruitment, we will stratify individuals based on their EHR-documented race/ethnicity into one of five groups: Non-Hispanic White, Black, Hispanic, Asian/Pacific Islander, Other. From these groups, we will select a list of 20 individuals to be recruited. In sum, the 100 individuals will be comprised of 20 individuals selected at random from 5 self-reported racial/ethnic groups, with the intent that each racial/ethnic group will have 10 individuals represented in the mailed Cologuard outreach and mailed FIT outreach (each group makes up 20% of the sample in each arm). This will ensure equal balance of participants from each racial/ethnic group in each trial arm.

Eligible individuals will be mailed a postcard briefly describing the study and asking patients to scan a QR code if they are interested in participating. The QR code will take eligible individuals to eConsent forms within REDCap, where they will be provided with informed consent and HIPAA Authorization forms that will need to be completed to participate in the study. Electronically completed and signed informed consent and HIPAA authorization forms will be required prior to randomization. HIPAA Authorization is necessary to release relevant patient information to Exact Sciences, the company that will mail and implement the Cologuard test, should the participant be randomized to that group. Additionally, HIPAA Authorization ensures participant electronic health records may be examined to measure the study's outcomes of interest over the course of study follow-up.

If individuals decline participation or do not sign HIPAA authorization and informed consent documents, they will be replaced by another eligible individual from the same EHR-documented race/ethnicity grouping. After agreeing to participate, individuals within each race/ethnic group will

be assigned randomly to the mailed Cologuard outreach and mailed FIT outreach arms, such that an equal number of individuals from each group is included in each trial arm. Recruitment will continue until a sample size of 50 individuals per trial arm (mailed Cologuard outreach and mailed FIT outreach) who consent to participation in the study is achieved.

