The primary study endpoint is colorectal cancer (CRC) screening completion within 3 months of randomization. We plan to measure this using Healthcare Effectiveness Data and Information Set (HEDIS) documentation to inform our CRC screening uptake variable. This variable will incorporate CPT, Healthcare Common Procedural Coding System (HCPCS), and ICD-9/10 coding to identify FIT or guaiac fecal occult blood tests (CPT: 82270, 82274; HCPCS: G0328), flexible sigmoidoscopy (CPT: 45330-45335, 45337-45342, 45345-45347, 45349, 45350; HCPCS: G0104; ICD-9: 45.24), colonoscopy (*CPT/HCPCS codes mentioned in **Table 1***; ICD-9: 45.22, 45.23, 45.25, 45.42, 45.43), CT colonography (CPT: 74261-74263) and FIT-DNA (Cologuard) tests (CPT: 81528, HCPCS: G0464). We will also conduct manual EHR review to validate our HEDIS-defined algorithm. After the initial EHR query to define our study population, we will do manual EHR review two times during the follow-up period, once in the first month after study start to test the HEDIS-defined algorithm and a follow-up review in the second month after study start to validate the final algorithm. At the end of 3 months of study follow-up we will use the validated final algorithm to query for CRC screening completion.

B. Secondary Endpoints

Aim 2 Pilot Trial Secondary Outcomes

In the pilot trial, we will measure multiple outcomes to assess feasibility of a larger trial. We will measure the total number of participants who opt out of the pilot as a recruitment outcome. We will also measure the number of participants with undeliverable Cologuard or FIT kits, known as mail fail rate, as an intervention outcome. Among those with abnormal Cologuard or FIT, we will measure the proportion who are referred to colonoscopy and proportion who complete colonoscopy. We will measure the proportion who are referred to colonoscopy and the proportion who complete colonoscopy via manual EHR review of participants with abnormal Cologuard or

FIT results. We will conduct the manual EHR review 3 months, 6 months and 9 months after randomization, only among randomized study participants (those who provided signed HIPAA authorization and informed consent).

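### The stated 80% power for a 15-point difference with 50 per arm is wrong: the plan's own inputs give about 37%, and the promised precision figure is missing

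*Combined protocol and SAP*

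**What the plan says.** The sizing text for the pilot is one paragraph under Summary of the Study Design, section E, Sample Size and Rationale. It begins by calling Aim 2 a feasibility study whose size was not chosen to give power for a test, and continues: "We instead assess precision of our primary outcome, CRC completion in 3 months, based on a projected sample size of 100", split 50 per group, with "a two-sided type I error alpha of 0.05". The next sentence claims "we will have 80% power to detect a ≥ 15 percentage point higher rate of completion in the Cologuard group" over the mailed FIT group, with FIT completion taken as 23%. The source of the 23% follows: "The assumption of mailed FIT completion is based on internal, UCSDHS data from prior mailed FIT outreach in 45 to 49 year olds".

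The endpoint is binary. Study Outcome Measurements, section A, says: "The primary study endpoint is colorectal cancer (CRC) screening completion within 3 months of randomization". Patient Population, section A, confirms the allocation of 50 per arm.

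Study Hypotheses and Objectives gives two further facts. The primary study hypothesis is that Cologuard outreach leads to higher uptake than mailed FIT outreach. The Aim 2 hypothesis is that the pilot will show a full trial to be feasible, help refine the outreach, and inform that trial's power and sample size.

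**The concern.** Fifty per arm is small for separating two proportions 15 points apart in the middle of the range, so 80% power looked implausible on sight. Every input is in the same paragraph, so the claim can be checked without outside information.

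Two things are at stake. First, the statement is made as fact about the primary outcome of a pilot that is meant to feed the sizing of the next trial. Someone who trusts it could read a non-significant result as evidence that Cologuard outreach adds nothing, and someone who repeats the calculation would undersize the full trial. Second, the paragraph promises an assessment of precision, which is the right basis for a pilot of this kind, and then reports none. The one quantitative statement offered in support of the sample size is the incorrect one.

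**Working it through.** **Inputs**, all from section E: n = 50 per arm; two-sided alpha 0.05 (z = 1.960); FIT rate p1 = 0.23; difference 0.15, so p2 = 0.38. The plan names no test, so several are tried.

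**Reproducing the stated 80%** (two-sample z-test, pooled variance under the null)

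- Mean rate = (0.23 + 0.38)/2 = 0.305
- SE under the null = √(2 × 0.305 × 0.695 / 50) = 0.0921
- SE under the alternative = √((0.23 × 0.77 + 0.38 × 0.62)/50) = 0.0909
- Power = Φ((0.15 − 1.960 × 0.0921)/0.0909) = Φ(−0.335) = **36.9%**

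The 80% is not reproduced. Other two-sided methods on the same inputs:

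| Method | Power |
|---|---|
| Unpooled z | 37.9% |
| Arcsine | 37.5% |
| Chi-square, exact enumeration of both binomials | 37.1% |
| Fisher's exact test, exact enumeration | 29.7% |
| Continuity-corrected z | 28.9% |

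**Could a slip in the inputs explain it?** Each row departs from what the plan states (normal approximation).

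| Departure | Power |
|---|---|
| One-sided 0.05, 50 per arm | 49.4% |
| 100 per arm, two-sided 0.05 | 63.6% |
| 100 per arm, one-sided 0.05 | 74.8% |
| One sample of 50 against a fixed 23%, two-sided 0.05 | 68.6% |
| One sample of 50 against a fixed 23%, one-sided 0.05 | 77.6% |
| One-sided alpha 0.20, 50 per arm | 78.8% |

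The last two come near 80%, but one drops the control arm and the other contradicts the stated alpha. No two-arm calculation at the stated alpha comes close.

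**Does stratification help?** Randomization is balanced within five race/ethnicity groups, 10 per group per arm. Simulating a Cochran-Mantel-Haenszel test gives about 37% power if all strata share the same rates. It gives about 41% if stratum FIT rates are spread from 5% to 50% around a mean of 23% (an assumption), with 15 points added in each.

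**What the design does offer**

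- Size needed for 80% power at 23% vs 38%: (1.960 × √(2 × 0.305 × 0.695) + 0.842 × √(0.1771 + 0.2356))² / 0.15² = 146.7, so **147 per arm** (294 in total). With continuity correction it is 160 per arm.
- Difference detectable with 80% power at 50 per arm: solving the power formula with p1 = 0.23 gives between 26.6 and 26.7 points, **about 27** (23% to about 50%).
- Half-width of the 95% confidence interval for the difference at 23% vs 38%: 1.96 × 0.0909 = 0.178, **about 18 points**. The largest possible value, with both rates at 50%, is 1.96 × √(0.5/50) = 0.196, about 20 points.
- Chance of a non-significant result if the truth is 23% vs 38%: 1 − 0.369 = **63%**, where the stated power implies 20%.

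**The case against.** The strongest reply is that the paragraph disclaims power. It says the pilot was not sized for hypothesis testing, the Aim 2 hypothesis is about feasibility, no test of the primary outcome is named, and no go/no-go rule depends on it. This stands as a limit on the consequence. A reader might infer that a null pilot will inevitably be taken as evidence against Cologuard outreach, or that 100 participants are too few. The documents support neither. They show a false power statement beside a superiority hypothesis, which could mislead, and they do not show that the pilot is too small for feasibility. The disclaimer does not make 80% true.

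A reader might also infer that the 23% cannot apply here, because only people who answer a postcard and sign electronic consent and HIPAA forms are randomized. The true control rate may well be higher. But the plan says only that the figure comes from internal data on prior mailed FIT outreach, and does not describe how those people were recruited or consented. The point also hardly matters: for control rates of 30% to 60% (an assumption), power for 15 points is 32% to 36%.

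Finally, one might conclude that the later trial should be sized on 15 points. The documents never call 15 points a target or an important difference. It appears only as the detectable difference attached to the incorrect power figure.

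It is also fair to say that 37% depends on the test. Across standard two-sided methods the range is about 29% to 38%, so the corrected text should name the test.

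**Conclusion.** The power statement is wrong as written. At the plan's own inputs power is about 37% by a pooled z or chi-square test and about 30% by Fisher's exact test, less than half the stated 80%. The planned 50 per arm is about a third of the 147 that the claim would require (50/147 = 34%). Separately, the precision that the paragraph says it assesses is not reported; it is about ±18 points for the difference at 23% vs 38%.

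The calculation assumes true rates of 23% and 38%, 50 analysed per arm, and an unstratified comparison. The plan states no allowance for loss, and losing participants from the analysis would lower power further. The arithmetic is certain. The consequence is a possibility: a non-significant result could be misread as no benefit. The sample size itself is not faulted for a feasibility pilot.

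**What to change.** Keep 100 participants and replace the power sentence in section E with text such as:

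> With 50 per arm, the 95% CI for the difference in completion has a half-width of about 18 percentage points at 23% vs 38% (at most about 20 points). Power for a 15-point difference is about 37% by a two-sided chi-square test (about 30% by Fisher's exact test), and 80% power is reached only for about 27 points. The comparison is for estimation, and non-significance will not be read as no difference.

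A short table of half-width and power over other control rates is optional.

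The cost is a wording change in one paragraph. It needs no extra participants and no change to procedures. The stated figure becomes less favourable, but the paragraph then delivers the precision assessment it announces.
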